Protocol Outline

Protocol Title: Intraop Cone-beam CT for Percutaneous Nephrolithotomy

Protocol Date: August 23, 2021

Principal Investigator: [name], [name]

Research Team: [name], [name]

I. Abstract

Percutaneous nephrolithotomy (PCNL) is a first-line treatment for kidney stones >2cm. Frequently, patients require multiple procedures to address their stone burden. The decision to proceed with a second-look procedure is based on follow-up CT imaging, which is obtained postoperatively. In this study, we propose the use of a portable CT scan technology to obtain follow-up imaging while the patient is still under anesthesia for the initial procedure. The goal of this study is to determine whether this allows the surgeon to identify residual fragments and render the patient stone-free within a single anesthetic event.

II. Background and Significance/Preliminary Studies

Percutaneous nephrolithotomy (PCNL) is considered a first-line management option for kidney stones larger than two centimeters. Unfortunately, because of the large stone burden, up to 70% of these patients are left with residual stone fragments after their initial PCNL.¹ Additionally, an estimated 20% to 60% of such patients ultimately require further interventions due to residual stone fragments.² The need for a subsequent procedure is determined by postoperative abdominal computed tomography (CT) imaging, which is routinely performed on the first postoperative day at this institution. The decision to proceed with a second procedure is based on findings from this postoperative CT scan.

Cone-beam CT (CBCT) is a novel portable imaging technique that can allow cross-sectional imaging to be obtained intraoperatively, rather than post-operatively.³ Incorporating this modality would allow the surgeon to determine whether the procedure should be continued, in the event of residual fragments, or if it can be safely concluded. This would obviate the need for dedicated postoperative CT scans and, more importantly, reduce the need for subsequent procedures and consequently decrease the patient's length of stay.

III. Study Aims

The purpose of this study is to determine whether using CBCT to perform an abdomen-pelvis CT scan immediately following initial PCNL, before the patient emerges from general anesthesia, allows the surgeon to determine whether additional work is needed or whether the procedure can be concluded without requiring further imaging or future interventions. Therefore, the primary outcome will be the rate of subsequent surgical intervention (i.e. "second-look" interventions) in patients undergoing CBCT.

IV. Administrative Organization

This study will be performed exclusively in the Main Operating Room area of Loyola University Medical Center.

V. Study Design

1. The study population will be patients undergoing initial PCNL, and they will be recruited to participate in this study prior to surgery.
2. Outcomes from this study will be compared with existing data on rates of second-look intervention at this institution.
3. **Our retrospective chart review of PCNL patients from 2018 and 2019 revealed a total of 178 PCNL patients, with a second-look intervention rate of 31.5%. We anticipate that use of CBCT will reduce our second-look intervention rate to 10%. However, despite being rendered radiographically stone-free with CBCT, we imagine patients may require second-look procedures for various reasons; we estimate the upper bound of this occurrence to be 15%. Assuming this, along with a power of 80% and a type I error rate of 5%, our study would be appropriately powered with 39 patients. We will aim to recruit 60 patients to allow for redundancy and unanticipated exclusions such as for reasons listed in VI.1.i.2.**

VI. Study Procedures

1. Subject selection procedures
 - i. Sampling plan
 1. Inclusion criteria:
 - a. Patients >18yo
 - b. Undergoing initial PCNL
 - c. **Stone fragmentation (laser/ultrasonic/mechanical) was performed during the procedure**
 2. Exclusion criteria:
 - a. **Patients who are deemed by the operating surgeon not to require any form of CT imaging, intra-operatively or post-operatively (for example, this can occur in the event of a single visible stone which is removed in its entirety under direct vision without requiring any fragmentation)**
 - b. Patients whose procedures are aborted for various reasons, including but not limited to bleeding, hemodynamic instability, equipment failure, and inadequacy of nephrostomy access
 - c. Patients whose habitus does not allow for the use of the CBCT machine
 - ii. Recruitment procedures
 1. **Patients undergoing initial PCNL will be recruited and provided protocol/consent materials at a preoperative**

outpatient clinic visit. Consent will be obtained by one of the research team members at the preoperative visit or in the preoperative area on the day of surgery.

2. The patient will not be required to attend any additional clinical appointments beyond standard care. The patient will not be compensated for their participation in the study.
2. Data collection procedures
 - i. **A retrospective chart review of first-look PCNL procedures from 2018-2019 will be performed to identify a matched-cohort (based on patient demographics and stone characteristics) that meets the inclusion and exclusion criteria.**
 - ii. Data will be prospectively collected for our study cohort. The determination of our primary outcome (need for repeat surgical intervention) will be made in our usual fashion: via shared decision-making between the patient and the surgical team on the day subsequent to the initial procedure.
 - iii. Data collected for both cohorts will include but not be limited to:
 1. Demographic factors (age, sex, race/ethnicity)
 2. Medical factors (patient height and weight, presence of medical comorbidities, surgical history, pertinent laboratory values)
 3. Stone factors (location, size, composition, and other characteristics)
 4. Surgical factors (length of procedure, blood loss, operative time, length of hospital stay, radiation dose)
 5. Surgical complications, ranked by Clavien-Dindo class
 - iv. All data will be entered into Loyola's secure RedCAP application.

VII. Safety Monitoring Plan

1. There are no additional anticipated patient safety issues associated with performing intra-operative CBCT when compared to standard post-operative CT imaging.
2. In another study using the same Medtronic O-arm CBCT system that is available at Loyola, it has been demonstrated that the radiation dose experienced by the patient from CBCT is lower than that from standard CT imaging.⁴
3. In regards to radiation safety for operating room staff, standard precautions will be taken which include but are not limited to: using lead aprons for sterile surgical staff, optimizing the placement of sterile and non-sterile surgical staff, using lead aprons for sterile surgical staff, and standing beyond a 2-meter distance from the iso-centre. Assuming one CT per surgical procedure, a liberal average of three procedures per week, and 48 work-weeks per year, an unprotected staff member would be expected to receive below 1.6 mSv a year at a distance of 2-meters from the iso-centre.⁴ This is far below the occupational exposure limit set at 50 mSv per year by OSHA (Occupational Safety and Health Administration).

VIII. Analysis Plan

1. The historical cohort and study cohort will be compared on a variety of demographic and surgical factors to ensure homogeneity between the groups. Chi-squared and Student's t-tests will be performed as appropriate.
2. The proportion of patients requiring a second-look procedure would be calculated for both our cohort under study and our historical cohort. These proportions would be analyzed with a chi-squared test to determine statistical significance.
3. We would also perform subgroup analyses on a variety of patient characteristics, including but not limited to BMI, stone size, stone composition, and stone location, to determine if certain patient populations are more likely to benefit from CBCT.
4. Data will be analyzed by exporting tables from RedCAP onto Loyola's secure research network drives. From there, data will be imported into SPSS and analyzed as appropriate by the research team.

IX. Literature Cited

1. Pearle MS, Watamull LM and Mullican MA: Sensitivity of noncontrast helical computerized tomography and plain film radiography compared to flexible nephroscopy for detecting residual fragments after percutaneous nephrostolithotomy. *J Urol* 1999; 162: 23.

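### The 80% power claimed for 39 patients is not tied to the comparison that will be made, and at 31.5% it fails at the protocol's own 15% upper bound

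*Combined protocol and SAP*

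**What the plan says.** Section V.3 takes its benchmark from a review of 2018 and 2019 already done, which "revealed a total of 178 PCNL patients, with a second-look intervention rate of 31.5" per cent. It does not say that these were initial procedures, or that the inclusion and exclusion criteria were applied. For the CBCT group it says "We anticipate that use of CBCT will reduce our second-look intervention rate to 10" per cent, then allows for other reasons to return: "we estimate the upper bound of this occurrence to be 15" per cent. It proceeds from there, "along with a power of 80% and a type I error rate of 5" per cent, to the statement that "our study would be appropriately powered with 39 patients". No test, sidedness or control-group size is given. The target of 60 is there to absorb redundancy and exclusions.

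The comparator is described in three other places. Section V.2 says outcomes will be "compared with existing data on rates of second-look intervention at this institution". Section VI.2.i describes a review still to be carried out, to "identify a matched-cohort (based on patient demographics and stone characteristics) that meets the inclusion and exclusion criteria". Section VIII.2 compares the study cohort with the historical cohort by chi-squared test and does not say whether that cohort is the matched one. VI.2.i is the only passage that explains how a comparison cohort is built.

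**The concern.** The sizing rate and the planned comparison group are not shown to be the same population. The eligibility criteria in VI.1.i require fragmentation, and they remove aborted procedures and patients judged to need no CT. Each of these could plausibly be related to the chance of a second procedure. Matching then fixes how many historical patients enter the test, and power depends on that number as well as on the rate.

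The trial has no concurrent control, so the primary conclusion rests on this one two-group comparison. If its real power is well below 80%, a null result would say little, and a reader of V.3 would not know that.

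**Working it through.** **Inputs.** Benchmark 31.5% of 178 (about 56 patients), CBCT rates of 10% and 15%, 5% type I error, 80% power, 39 patients and a target of 60, all from V.3. Chi-squared test of two cohorts from VIII.2. I take the test as two-sided. Matched cohorts of 39, 60 and 78 are my illustrations of 1:1 and 1:2 matching.

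**Step 1: the stated 39.** Several routes come close, and none is identified by the document.
- One-sample arcsine, one-sided, 31.5% taken as known, against 15%: h = 2·arcsin√0.315 − 2·arcsin√0.15 = 0.3964; n = ((1.6449 + 0.8416)/0.3964)² = 39.35.
- Two-sample, one-sided, unpooled variance, 178 controls, 15%: 40.
- Two-sample, two-sided, three controls per CBCT patient, 10%: 38.7, so 39.

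The two-sided pooled (chi-squared) calculation against a fixed 178 gives 35 at 10% and 75 at 15%, and neither is 39.

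**Step 2: power of the planned test at 31.5%.** For n₀ historical patients at rate p₀, n₁ CBCT patients at rate p₁ and pooled rate p̄, the normal approximation is

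power = Φ{(p₀ − p₁ − 1.96·SE₀)/SE₁}, with SE₀ = √[p̄(1 − p̄)(1/n₀ + 1/n₁)] and SE₁ = √[p₀(1 − p₀)/n₀ + p₁(1 − p₁)/n₁].

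- 39 v 178 at 15%: p̄ = (56.07 + 5.85)/217 = 0.2853; SE₀ = 0.0798; SE₁ = 0.0669; (0.165 − 0.1564)/0.0669 = 0.128; power 55%.
- 39 v 39 at 10%: p̄ = 0.2075; SE₀ = 0.0918; SE₁ = 0.0885; (0.215 − 0.1799)/0.0885 = 0.396; power 65%.

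Exact power, summing binomial probabilities over all tables where the Pearson statistic is significant at two-sided 5%:

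| CBCT v historical | CBCT rate 10% | CBCT rate 15% |
|---|---|---|
| 39 v 178 | 85% | 57% |
| 39 v 78 | 77% | 49% |
| 39 v 39 | 67% | 42% |
| 60 v 178 | 95% | 73% |
| 60 v 60 | 85% | 59% |

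With 39 CBCT patients and a 15% rate, I checked every comparator size from 20 to 178; exact power never exceeds 57%. By the normal approximation, 1:1 matching needs 55 per group at 10% and 102 at 15% for 80% power.

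**Step 3: what eligibility could do to the benchmark.** The documents give no counts, so this is assumption only. If a share a was aborted with return risk r, and a share b had no fragmentation or no CT with return risk s, the eligible rate is (0.315 − a·r − b·s)/(1 − a − b). Take a = 5–10%, r = 70–100%, b = 10–20%, s = 0–5%, with both exclusions applied together.
- Lowest: (0.315 − 0.10 − 0.005)/0.80 = 26%.
- Highest: (0.315 − 0.035 − 0)/0.75 = 37%.
- Midpoints: (0.315 − 0.06375 − 0.00375)/0.775 = 31.9%.

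In counts (normal approximation, power at 10% / 15%):
- Removing 40 patients, 20 of them with a second look, leaves 36/138 = 26.1%, and 39 v 138 has power 58% / 28%.
- Removing 30 with no second look leaves 56/148 = 37.8%, and 39 v 148 has power 97% / 82%.

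**The case against.** Sizing from a crude institutional rate is ordinary practice when nothing better is at hand, and V.3 does not claim that the rate is exact. At the anticipated 10%, 39 patients against all 178 do exceed 80%. If all 60 recruits were evaluable, 1:1 matching would also suffice at 10%. These points stand. They do not rescue the 15% case, which V.3 states immediately before its power claim, and the margin from 39 to 60 is already assigned to exclusions.

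Three stronger readings are tempting, and the documents do not support them.
- A reader might infer that the matched cohort's rate does differ from 31.5%, and in a known direction. Neither its rate nor its size is reported. The exclusions pull against each other, and plausible midpoints return almost the planned figure.
- A reader might infer that selected CBCT patients will be tested against an unfiltered 31.5%, which would build in bias. VI.2.i asks for a matched comparator under the same criteria, VIII.1 checks that the groups are alike, and VIII.2 compares two cohorts rather than testing against a fixed rate. Only the loose wording of V.2 leaves room for that reading.
- A reader might infer that 39 is an arithmetical slip or came from one particular formula. Several calculations land near it, and test and sidedness are unstated.

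**Conclusion.** The point holds as a gap between the power statement and the planned test. V.3 does not establish 80% power for a comparison with a matched, eligible cohort whose size, ratio and rate are unstated. With the benchmark held at 31.5%, the shortfall needs no assumption about eligibility: 39 patients have at most 57% power at a CBCT rate of 15% for any comparator of up to 178, and 67% to 77% at 10% under 1:1 or 1:2 matching. Even 60 evaluable patients against all 178 reach only 73% at 15%.

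This rests on a two-sided 5% chi-squared test of independent groups and on reading the historical cohort in VIII.2 as the one built in VI.2.i. If the eligible rate proves higher, near 38%, a large unmatched pool could support 80% at 15%. If it is near 26%, power falls short even at 10%. The net direction is unknown until the charts are tabulated.

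**What to change.** - Use one comparator definition in V.2, V.3, VI.2.i and VIII.2: the 2018–2019 initial PCNLs that meet VI.1.i on grounds verifiable from the chart.
- Tabulate the second-look rate and denominator of that eligible pool and put both in V.3. This can be done now. A matched subset depends on who is enrolled, so its own rate cannot be fixed in advance.
- State whether the whole pool or a matched subset is tested and, if matched, at what ratio.
- Restate the power of the two-sided chi-squared test for 39 and 60 patients, at CBCT rates of 10% and 15%, with that comparator size and rate.

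The cost is re-tabulating charts already reviewed, plus wording changes. The stated power will probably look less favourable, and 80% at a CBCT rate of 15% should no longer be claimed unless the tabulated eligible rate supports it. Restating the power needs no extra patients, but reaching 80% at 15% might.

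### The 15% in V.3 bounds second looks among patients cleared on CBCT, not the whole-cohort rate being tested, and even at 15% overall 39 patients do not give 80% power

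*Combined protocol and SAP*

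**What the plan says.** Section V.3 starts from the institution's 2018–2019 chart review, which "revealed a total of 178 PCNL patients, with a second-look intervention rate of 31.5" per cent. It then states an expectation for the cohort as a whole: "We anticipate that use of CBCT will reduce our second-look intervention rate to 10" per cent. The next sentence turns to a narrower group: "despite being rendered radiographically stone-free with CBCT, we imagine patients may require second-look procedures for various reasons". The bound on that occurrence leads directly into the power statement: "we estimate the upper bound of this occurrence to be 15%. Assuming this, along with a power of 80" per cent. That statement continues: "along with a power of 80% and a type I error rate of 5%, our study would be appropriately powered with 39 patients". The target is then raised: "We will aim to recruit 60 patients to allow for redundancy and unanticipated exclusions".

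Section III defines the primary outcome as the rate of subsequent surgical intervention "in patients undergoing CBCT", with no restriction to those cleared. Section VIII.2 compares that proportion with the historical cohort by a chi-squared test. Section VI.2.i says the historical comparator will be a matched cohort and does not give its size. No formula, sidedness, stone-free share or second-look rate for uncleared patients is given.

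**The concern.** The 15% and the primary outcome have different denominators. The 15% is attached to patients who are stone-free on CBCT. The outcome is counted in everyone who has CBCT, including patients whose remaining fragments are seen on the scan but cannot be cleared in the same session. V.3 has no term for that second group. Completed cases with stone left behind are not excluded under VI.1.i.2, and whether the surgeon can achieve clearance in one anesthetic is what the Abstract says the study sets out to learn.

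If the 15% was used as the whole-cohort rate, calling it an upper bound is justified only when the uncleared group is essentially empty. Any second looks in that group above a 15% rate raise the tested rate and shrink the difference from 31.5%. A null result could then be read as CBCT failing, when the planning effect had left those patients out.

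**Working it through.** **Inputs from the documents.** Control rate 31.5% of 178; CBCT rate 10% (anticipated) or 15% (upper bound); 80% power; 5% type I error; 39 patients, 60 to be recruited (all V.3); chi-squared test (VIII.2). **Assumed.** Two-sided testing; 178 controls available; the uncleared share and its second-look rate, which the documents do not give.

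**1. The plan's 39.** The closest match is a one-sample, one-sided arcsine calculation with 15% as the whole-cohort rate:

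- h = 2·arcsin√0.315 − 2·arcsin√0.15 = 1.1918 − 0.7954 = 0.3964
- n = ((1.645 + 0.842) / 0.3964)² = 39.35

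The match is not unique. A one-sided unpooled z-test against a fixed 178 controls gives 40. Two-sided one-sample Wald calculations give 37, either at 15% with that rate's variance or at 10% with the null variance. So 39 fits best with 15% as the cohort rate, but that use is inferred and not stated. The planned test does not reproduce it: a two-sided pooled chi-squared test against a fixed 178 controls needs 75 CBCT patients at 15%, or 35 at 10% (normal approximation).

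**2. From the conditional rate to the whole cohort.** Let s be the share stone-free on CBCT and q the second-look rate among the rest. Then

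overall rate = s × 15% + (1 − s) × q,

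which equals 15% only if s = 100% or q = 15%. Illustrative values, using the 20–60% re-intervention range in section II and 100% as an extreme:

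- s = 90%, q = 20%: 13.5% + 2% = 15.5%
- s = 95%, q = 100%: 14.25% + 5% = 19.25%
- s = 90%, q = 60%: 13.5% + 6% = 19.5%
- s = 90%, q = 100%: 13.5% + 10% = 23.5%
- s = 80%, q = 60%: 12% + 12% = 24.0%

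With q = 100%, the difference from 31.5% disappears when the uncleared share reaches (0.315 − 0.15) / (1 − 0.15) = 19.4%.

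**3. Power of the planned test.** Full binomial enumeration of the two-sided Pearson chi-squared test at 5%, 178 controls at 31.5%:

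| Whole-cohort CBCT rate | 39 patients | 60 patients |
|---|---|---|
| 10% | 85% | 95% |
| 15% | 57% | 73% |
| 15.5% | 53% | 70% |
| 19.25% | 32% | 45% |
| 23.5% | 15% | 21% |

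**4. Size of the comparator.** At 15%, the normal approximation gives 55% / 73% with 178 controls. With a matched cohort equal in size to the CBCT group (39 v 39, 60 v 60) it gives 41% / 57%.

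**The case against.** The strongest reply is that V.3 has already given a whole-cohort figure, 10%, set directly against the cohort-wide 31.5%. On that view the 15% is a cautious cap on the 10%, and full clearance is not assumed: 90% × 10% + 10% × 60% = 9% + 6% = 15%. This reading is possible and it stands as an alternative. What weakens it is that the only reason V.3 gives for going above 10% is second looks in patients who were cleared. A third reading takes the 15% as the share of all CBCT patients who are cleared and still return; uncleared patients would then have to be added on top.

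The reply also limits the point in four other ways, and each limit is accepted.

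- A reader might infer that the planned effect could not occur even if all the protocol's beliefs were right. The documents do not support this: the anticipated 10% is one of those beliefs, and at 10% even 39 patients give 85% power.
- A reader might add fragments that CBCT missed to the uncleared group. Those patients are stone-free on the scan, so their second looks already fall within the 15%. Only fragments seen and not cleared are left out, and VI.1.i.2.b removes part of that group by excluding aborted procedures.
- A reader might take the Background's statement that "up to 70% of these patients are left with residual stone fragments after their initial PCNL" as the uncleared share. It describes PCNL in general, not patients scanned and re-treated in the same session, so it does not estimate that share.
- The effect can be trivial. With 10% uncleared and a 20% second-look rate among them, the overall rate is 15.5% and power is 53% / 70%, against 57% / 73% at 15%.

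Finally, the shortfall at exactly 15% comes from the calculation behind 39 not being the planned test. It does not come from the denominator, which can only make matters worse.

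**Conclusion.** The point holds in a limited form. As written, V.3 carries a rate defined among cleared patients into a power statement about all CBCT patients, and does not say whether 15% was also meant to cap the whole cohort. That the plan assumes every patient is cleared is an inference the text does not settle.

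The firm numerical result concerns the 15% itself. Taken as the whole-cohort rate, it gives 57% power with 39 patients and 73% with 60 under the planned test, not 80%. This rests on two-sided testing at 5% and on 178 controls; the matched cohort may be smaller. How much further power falls because of uncleared patients cannot be fixed from the documents. Over the illustrated range up to 23.5%, it runs from a few percentage points to most of the power. At the anticipated 10%, power is adequate.

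**What to change.** Rewrite the power paragraph in V.3 to:

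- state the planning rate as a second-look rate in all CBCT patients, built from two declared parts: patients cleared who return for other reasons, and patients not cleared in the session;
- state the denominator of the 15%, and call it an upper bound only if it is meant for the whole cohort;
- name the formula and sidedness, and replace the claim of 80% power with 39 patients by the power of the planned chi-squared test over whole-cohort rates of about 10–24%, for the numbers of CBCT patients and matched controls actually available.

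The cost is one paragraph. The target of 60 need not change on this account. The downside is that the stated power will look less favourable.

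### At the 15% rate the protocol names, 39 patients give at most 57% power, not 80%, for the planned two-sided chi-squared test at the 31.5% control rate; 60 evaluable give at most 73%

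*Combined protocol and SAP*

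**What the plan says.** The sample-size justification is a single paragraph, section V (Study Design), item 3. The chart review of 2018 and 2019 "revealed a total of 178 PCNL patients, with a second-look intervention rate of 31.5"%. For the new cohort, "We anticipate that use of CBCT will reduce our second-look intervention rate to 10"%. The next sentence allows for second looks in patients whom CBCT shows to be stone-free: "we estimate the upper bound of this occurrence to be 15"%. The power claim comes straight after, taking that as its assumption: "along with a power of 80% and a type I error rate of 5%, our study would be appropriately powered with 39 patients". Recruitment is set higher: "We will aim to recruit 60 patients to allow for redundancy and unanticipated exclusions".

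Two other places decide which test this power belongs to. Section VI.2.i makes the comparator a chart review that will "identify a matched-cohort (based on patient demographics and stone characteristics) that meets the inclusion and exclusion criteria", with no ratio or size given. Section VIII, item 2 computes the second-look proportion in both cohorts and adds: "These proportions would be analyzed with a chi-squared test to determine statistical significance".

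**The concern.** A chi-squared test between two cohorts carries sampling error from both, so the historical 31.5% is an estimate and not a fixed constant. For a difference of 31.5% against 15%, 39 patients looks far too few whatever the number of controls.

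This paragraph is the only sample-size argument for the primary outcome. If the CBCT rate were 15%, the second-look rate would have roughly halved, and a two-sided test on 39 patients would still miss it about half the time. A non-significant result from a study described as adequately powered could then be read as evidence against CBCT.

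**Working it through.** **Inputs.** From V.3: control rate 31.5%, CBCT rate 15% (upper bound) or 10% (anticipated), power 80%, type I error 5%, 39 patients needed, 60 recruited, 178 historical patients. From VIII.2: chi-squared test. Assumed, because not stated: two-sided, no continuity correction, and comparator sizes from 1:1 up to all 178.

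**Step 1. Try to reproduce 39 at 15%.** With k controls per CBCT patient and p̄ = (p₁ + k·p₀)/(1 + k), the pooled formula is

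n = [z₀.₉₇₅·√(p̄(1−p̄)(1+1/k)) + z₀.₈₀·√(p₁(1−p₁) + p₀(1−p₀)/k)]² / (p₀−p₁)²

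At 1:1, p̄ = 0.2325 and n = [1.960·√0.3569 + 0.8416·√0.3433]² / 0.165² = 101.7, so 102 per group.

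- Two-sided at 15%: 102 (1:1), 79 (2:1), 71 (3:1, which would need 213 controls, more than exist), or 75 against a fixed 178.
- One-sided at 15%: 80 (1:1), or 54 against a fixed 178.

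None of these is near 39. Only methods other than the planned test come close: a one-sided, one-sample arcsine calculation treating 31.5% as known gives 39.3 (so 40), a one-sided unpooled Wald calculation against 178 gives 40, and a two-sided one-sample calculation using only the variance at 15% gives 36.8 (so 37).

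**Step 2. Try to reproduce 39 at 10%.** Two-sided, the same formula gives 55 (1:1), 43 (2:1), 35 against a fixed 178, and at 3:1, with p̄ = 0.26125,

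n = [1.960·√0.2573 + 0.8416·√0.1619]² / 0.215² = 38.4, so 39.

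The figure can therefore be matched at 10% with three controls per patient, but the protocol names neither as its basis.

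**Step 3. Power actually delivered.** Normal approximation for 39 against 178 at 15%: p̄ = (178×0.315 + 39×0.15)/217 = 0.2853; standard error under the null 0.07984, under the alternative 0.06694; (0.165 − 1.960×0.07984)/0.06694 = 0.127; power 55%. Exact power sums the two binomial probabilities over every table that the uncorrected Pearson test rejects at 5%:

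| CBCT v controls | 15%, two-sided | 15%, one-sided | 10%, two-sided |
|---|---|---|---|
| 39 v 39 | 41.6% | 54.0% | 67.4% |
| 39 v 78 | 49.3% | 63.5% | 77.3% |
| 39 v 117 | 53.9% | 66.9% | 82.0% |
| 39 v 178 | 56.5% | 70.1% | 85.0% |
| 60 v 60 | 58.6% | 70.4% | 85.0% |
| 60 v 120 | 69.2% | 80.3% | 93.0% |
| 60 v 178 | 73.1% | 83.7% | 95.1% |

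Exact power does not rise smoothly with the number of controls, so every comparator size was checked.

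- At 15% with 39 patients and 39 to 178 controls, two-sided power lies between 40.9% and 57.3%; the one-sided maximum is 71.2%.
- At 15% with 60 patients and 60 to 178 controls, two-sided power lies between 58.3% and 73.4%.
- At 10% with 39 patients, two-sided power first touches 80% at 90 controls and stays there from 99 upward.
- A Yates correction or Fisher's exact test lowers the 15% figures: 47.6% and 51.8% for 39 v 178, 67.1% and 70.1% for 60 v 178.

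**Step 4. Size needed at 15%, two-sided.** Against all 178 controls, the normal approximation gives 75 CBCT patients; exact power first reaches 80% at 74.

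**The case against.** The best defence is that the sponsor meant 10%, the rate it actually anticipates. At 10% with 3:1 controls the standard formula gives 39, the 117 controls fit within the 178, and exact power is 82%. The fault would then be undocumented assumptions, not wrong arithmetic. This is a live possibility, but it does not support the sentence as written. The 15% is the nearest antecedent and would otherwise play no part in the calculation. The ratio appears nowhere, and a 1:1 matched cohort gives only 67% two-sided even at 10%.

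Second, 60 patients will be recruited, not 39. With 60 evaluable, power at 10% is at least 85% at each ratio in the table, and a one-sided test at 15% reaches 80% with 120 controls. Both points stand, and they are why the target can be kept. But 60 is the count before exclusions, some of which (an aborted procedure, no CT needed) become known only at surgery, and no one-sided test is specified.

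Third, the control rate may not be 31.5% once the 178 have been screened for eligibility and matched. It could move either way, so the ceilings describe the protocol's stated inputs and not the study's eventual power. That condition is accepted.

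Finally, the 15% could be read as applying only to patients already stone-free on CBCT. The overall rate could then be higher still, which does not help the claim.

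**Conclusion.** The concern holds. With a control rate of 31.5%, a CBCT rate of 15% and the planned chi-squared test taken as two-sided at 5%, 39 patients give 41% to 57% power depending on the number of controls, against the 80% stated. The test would miss the difference in 43% to 59% of such trials. With 60 evaluable patients the range is 58% to 73%, or 27% to 42% missed.

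The shortfall at 39 does not depend on sidedness; the shortfall at 60 is specific to the two-sided test. At 10%, the claim for 39 holds two-sided only with about 100 or more controls, a condition the protocol does not state. The actual origin of 39 cannot be determined from the text.

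**What to change.** Keep the recruitment target of 60 and remove the statement that 39 patients give 80% power. In V.3, state the assumed CBCT rate, the sidedness, the test (with or without continuity correction) and the comparator size or matching ratio, consistent with VI.2.i and VIII.2. Possible wording:

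> Two-sided 5% chi-squared test without continuity correction, control rate 31.5%. With 60 evaluable CBCT patients and 60, 120 or at most 178 eligible controls, power is 85%, 93% or 95% if the CBCT rate is 10%, and 59%, 69% or 73% if it is 15%. Sixty patients do not reach 80% power at 15%.

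If a one-sided test is intended, say so and give its figures instead. Once the eligible matched comparator is known, recompute with its size and second-look rate. If 80% two-sided power at 15% is wanted, the requirement is about 75 evaluable CBCT patients against 178 controls, 79 at 2:1 or 102 per group at 1:1.

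The cost is protocol wording, an advance commitment on sidedness and matching ratio, and a less favourable stated power. Keeping 60 needs no extra patients.
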